Main inclusion/exclusion criteria:	Inclusion: Symptoms of FI, aged over and including 18, capacity to consent, male/female. Exclusion: anal cancer, anal surgery in the last 3 months, acute/painful perianal disease.
Statistical methodology and analysis:	Non-inferiority testing of MAPLe in the assessment of FI will be performed using Bland Altman method. MAPLe will be tested against HRAM and AUS.
	Participants will be grouped according their pathology: Fistula/chronic perianal disease, Obstetric injury <12 months, Obstetric injury >12 months, neuropathic sphincter. Correlation studies and regression analysis to identify which groups benefitted from MAPLe assessment.
	The clinical utilisation of MAPLe will be determined by the outcome of an expert panel.
	Comparative analysis of participant pre and post treatment MAPLe results will identify if targeted treatment has been achieved.

3. Background and Rationale

Burdon of Disease

Faecal incontinence (FI) is defined as the involuntary passage of gas, liquid or solid stool. The symptom is experienced by an estimated 1-10% of the population. FI is associated with a multitude of disease pathologies and prevalent in vulnerable patient groups, the elderly, learning disabilities or severe co-morbidities, and most prevalent in multiparous females. The degree of symptomatic severity is varied and can result in psychological destress and social withdrawal, severely impacting quality of life in up to 22% of suffers(1).

There is significant economic burden associated with FI. Health economic studies have identified US\$4110 as an average annual cost per person, with an increased cost associated with increased symptom severity(2). Further studies estimated a US \$11 billion annual expenditure and a 55% increase in personal cost of health for sufferers(3). Treatment is symptom orientated, further research would improve understanding of the symptom and direct treatment for more effective outcomes.

Anatomy and Physiology of the Pelvic Floor

FI is the result of impairment to the structure or function of the pelvic floor(4). The pelvic floor, levator ani, is a sheet of muscle supporting the weight of the abdominal cavity. It is divided into four muscle groups: pubococcygeus, ilio-coccygeus, coccyges and puborectalis, assisting the maintenance of faecal and urinary continence.

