Structural assessment of the anal sphincter is performed using an anal ultrasound (AUS). The AUS probe is placed into the anal canal. The transducer at the tip of the probe emits sound waves at a frequency between 2.5-6MHz, these reflect against the surrounding tissue and received by the transducer. The volume of sound waves reflected is dependent on the density of the tissue surrounding the probe. The differing structural integrities of the IAS and EAS give distinct appearances. The IAS is seen as a hypoechoic band approximately 1-3 mm in thickness. The EAS appears as a hyperechoic band surrounding the IAS with a thickness of 4-10mm. Abnormalities seen within each band such as lucencies or opacities represent pathology(12). Due to its low risk, low cost and high sensitivity, AUS is the imaging modality of choice for assessing the anal sphincter(13).

Functional assessment of the anal canal is undertaken using anorectal manometry. The technique measures the closing pressures of the anal canal. The test is performed using a probe with between 6-12 pressure sensors along its length. The manometry system can either be solid state or water perfused(14).

The probe is placed within the anal canal and pressures within the anal canal are recorded at rest, voluntary contraction and coughing. The pressures are measured in mmHg and represents the cross-sectional pressure of the canal at each level. The individual structures attributing to the pressure are not identified and the results are representation of the pressures of the pelvic floor as a whole.

Studies have been performed to identify a range for normal results of pressures within the anal canal. The results are dependent on gender and parity. Carrington et al undertook a study of 112 asymptomatic participants using high resolution anal manometry (HRAM) and identified a mean resting pressure of 33-110mmHg in females and 33-114 mmHg in males(15). Further studies have found disparity between age groups (16). Therefore, results require close and careful interpretation by the clinician, taking into account patient symptoms.

Treatment

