Studies performed at other centers have investigated the use of surface electrodes (sEMG) on probes(34) placed anally to identify abnormalities or abnormal variants in the innervation and propagation of stimulus within the EAS(35). The anal probes have a series of circumferential sensors that identify the origin and direction of propagation of an action potential. The origin correlates to the

location of an NMJ and innervation zone(19). This technique has been used to investigate asymmetric innervation of the anal canal, particularly important in obstetric medicine(36), but has not progressed from research into clinical utilisation.

The MAPLe device is a new medically certified device distributed by Novuqare using the principals of sEMG in the diagnosis and management of pelvic floor complaints (figure 1).

Figure 1 MAPLe device: anal probe, sEMG detector and charging station.

The probe l has 24 surface electrodes positioned in circumferential bands along its length (figure 2), it is placed in the anal canal. Each sensor detects the sEMG activity in mV for the most proximal muscle fibers (figure 3).

Figure 3 MRI of pelvis with anal probe in situ, confirming correct placement for sEMG detection.

The results are analysed by the receiver to provide numerical values. The values are displayed as a target shaped diagram depicting locational functionality (figure 4 & 5), giving a clear representation of precise areas of weakness in the pelvic floor.

Figure 4 The results can be displayed in three views.

Figure 5 Sensors are grouped together according to the muscle they represent.

The results are displayed on a hand held device in both numerical and diagrammatic formats (figure 6).

Figure 6 Results are displayed on screen in greyscale on target or numerical value.

An independent study tested MAPLe on 229 asymptomatic healthy participants. The study confirmed accurate probe placement to ensure sEMG correlated with correct muscular group, and identified a normal range (27). MAPLe is currently used to provide biofeedback for patients with FI by identifying and targeting muscles with reduced sEMG via visual and electrical stimulation.

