11.1 Primary Outcome

They primary outcome is to determine which participant groups benefit from assessment with MAPLe. Benefit will be determined by correct identification of abnormalities in symptomatic participants using MAPLe, correlation between symptom profile and MAPLe results, and the outcome of the expert panel. It will be measured once the end of recruitment is reached.

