11.5 Statistical analysis

11.5.1 Primary outcome analysis

Non-inferiority testing of MAPLe will be performed using Bland-Altman method. Correlation between MAPLe and AUS for location of sphincter abnormality will be identified. Correlation between MAPLe and HRAM for functional abnormalities will be identified.

Participants will be allocated a patient group dependent on the cause of FI:

- □ Fistula/ chronic perianal conditions
- \Box Obstetric injury <12 months
- \Box Obstetric injury > 12 months
- □ Neuropathic

Each group will be analysed using correlation studies and regression analysis to determine which groups benefit from MAPLe assessment.

The clinical benefit of the addition of MAPLe assessment will be determined from the analysis of the results of the expert panel.

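### Correlation is the only method named for comparing MAPLe with AUS on location of abnormality; it does not measure whether the two tests find it in the same place

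*Combined protocol and SAP*

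**What the plan says.** Section 11.5.1 gives location one sentence: "Correlation between MAPLe and AUS for location of sphincter abnormality will be identified". It does not name a coefficient, a unit of location, a tolerance for a match, or a rule for participants with no abnormality or with several. No other section supplies these.

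The same section also states that "Non-inferiority testing of MAPLe will be performed using Bland-Altman method". The Summary (section 2) adds that "MAPLe will be tested against HRAM and AUS". Neither sentence is tied to location.

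Section 11.1 lists three elements of benefit. The first is "correct identification of abnormalities in symptomatic participants using MAPLe"; the others are correlation with symptoms and the expert panel.

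Section 3 describes the measurements. The MAPLe probe has "24 surface electrodes positioned in circumferential bands along its length", and its values are "displayed as a target shaped diagram depicting locational functionality". For AUS, in the internal and external sphincter, "Abnormalities seen within each band such as lucencies or opacities represent pathology". How position is coded is not stated for either test.

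**The concern.** Identifying an abnormality correctly is a question of accuracy or agreement: where AUS shows an abnormality, does MAPLe flag the same place, and where AUS shows none, does MAPLe stay silent? Correlation asks something else, namely whether positions on one test rise and fall with positions on the other.

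The two can part company. A coefficient depends on how widely abnormalities are spread and on how position is coded, and it ignores a constant displacement. It also needs a position from both tests, so missed abnormalities and false alarms drop out. Those are the errors that the first criterion in 11.1 has to count. At stake is whether this strand of the primary outcome can be answered from the analysis as written.

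**Working it through.** **1. The plan's own figure.** None is given for location. The only sample-size figure in 11.3 reproduces as 4 groups × 30 = 120, but it does not rest on precision of location agreement, and this point does not depend on it.

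**2. What holds without assumptions about coding.**
- A coefficient on positions uses pairs (x, y). Of the four possible results (both tests positive, AUS only, MAPLe only, neither), only the first gives a pair.
- For any constant shift k, corr(x, x + k) = 1. A coefficient cannot see a constant displacement.

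**3. Illustration; all inputs here are assumptions.** True position T is normal with SD 1 h. AUS = T rounded to the hour. MAPLe = T + error, rounded, with error SD s. Both are coded 1 to 12. Distance is min(|d|, 12 − |d|). With 400,000 simulated pairs:

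| Centre of positions | s | Within 1 h | Pearson r |
|---|---|---|---|
| 12 o'clock | 0.5 h | 99% | 0.64 |
| 12 o'clock | 1 h | 85% | 0.41 (Spearman 0.23) |
| 6 o'clock | 0.5 h | 99% | 0.83 |
| 6 o'clock | 1 h | 85% | 0.67 |

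The 6 o'clock rows can be checked by hand, taking 1/12 as the rounding variance: r ≈ 1/√[(1 + 1/12)(1 + s² + 1/12)].
- s = 0.5: 1/√(1.0833 × 1.3333) = 1/1.202 = 0.83.
- s = 1: 1/√(1.0833 × 2.0833) = 1/1.502 = 0.67.

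Reading error is the same at both centres; only the place where the coding breaks differs. Positions uniform round the clock give about 0.81 and 0.65. Exact-hour agreement at s = 0.5 is only 61%, so calling those readings good depends on the one-hour tolerance.

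**4. Constant 3-hour rotation, on clock hours.**
- AUS at 4, 5, 6 and MAPLe at 7, 8, 9: r = 1, no location correct.
- AUS at 1 to 9 and MAPLe at 4 to 12: r = 1, no location correct, every error 3 h (90 degrees).
- Positions centred on 12 with SD 1 h: r = −0.59.
- Positions uniform round the full clock: r = −0.13.

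So r = 1 under rotation arises only if no position crosses 12/1.

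**5. Would a better coefficient or coding rescue it?**
- A circular correlation removes the 12/1 break, but a constant rotation leaves it unchanged, so it still equals 1 in the rotation examples.
- Recode 11, 12, 1 as −1, 0, +1, equally likely, with errors of −1, 0, +1 equally likely. Every reading is within 1 h. The variance of position is 2/3 and of the reading 4/3, so r = (2/3)/√(2/3 × 4/3) = 0.71 (simulated mean 0.70 at n = 30). The wrap-around has gone, but r remains well below 1 because the range is narrow.

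**The case against.** The strongest reply is that the plan does not commit to any coefficient on clock hours. The word may be a clinician's term for correspondence; section 3 uses it loosely when it says that sEMG matched the right muscle group. Location might be recorded by muscle group, sphincter layer, level along the canal or sector, since section 3 mentions sensors grouped by muscle and bands along the probe. This stands in part. A reader might infer that the plan will treat 12 and 1 o'clock as eleven units apart, but the documents never mention clock positions, so that cannot be charged to the plan. What survives is that the only term used denotes association and that nothing defines a match.

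A second reply is that the figures depend on the scenario. That is correct: the lowest values put abnormalities exactly at the coding break. A reader might also infer that a misrotated probe would generally yield perfect correlation. Step 4 shows otherwise, and the documents contain no evidence of a systematic orientation error.

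A third reply is that Bland-Altman already covers agreement. It does not cover location. It is attached to non-inferiority and needs two measurements in the same unit, whereas MAPLe reads sEMG in mV and AUS is an image.

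Finally, a sector analysis needs inputs that the plan lacks: a MAPLe cut-off per sector and a common orientation. A fixed grid also penalises near misses across a boundary. Both points stand and shape the fix.

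**Conclusion.** The concern holds in a limited form. Correlation, as written in 11.5.1, cannot show that MAPLe identifies AUS abnormalities in the right place, and a coefficient on positions leaves out the participants in whom the tests disagree about whether an abnormality exists. That conclusion needs no simulation.

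The size of the distortion in this study cannot be determined. The values of 0.41 to 0.83 rest on assumed clock-hour coding, an assumed spread and assumed reading error. They show only that near-identical agreement can produce quite different coefficients. They do not predict what the study will find.

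A reader might also infer that the whole primary outcome is undermined. The documents do not support that: location is one part of one of three benefit criteria in 11.1. The method should be changed, and the change is cheap if made before location data are collected.

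**What to change.** Replace the location sentence in 11.5.1 as follows.

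- **Unit.** Name the same circumferential sectors for both tests in advance and put them on the CRF. Record each sector as normal or abnormal on AUS and on MAPLe.
- **Orientation.** Record probe orientation at the MAPLe assessment so that the sectors line up with AUS. The MAPLe procedure in Appendix 5 has no such step. Section 8.3 places AUS at UCLH in radiology, apart from the physiology session, so a shared reference is needed.
- **Threshold.** State in advance what makes a MAPLe sector abnormal. The normal range that section 3 reports from 229 asymptomatic participants is one possible source. The protocol gives no values from it, and the reference number attached to it leads to a trial of tibial nerve stimulation, so the citation must be corrected first.
- **Analysis.** Report sector-level sensitivity, specificity and kappa against AUS. Use confidence intervals that allow for several sectors per participant, for example a bootstrap that resamples participants.
- **Who is included.** Keep participants with no abnormality on one or both tests.
- **Sensitivity analysis.** Repeat with an adjacent sector counted as a match, to show how far the result depends on sector boundaries.

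The cost is a CRF grid, an orientation note at each MAPLe assessment, agreement on the threshold, and slightly more analysis work. The sector and orientation data should be captured when the tests are done, because they may not be recoverable afterwards.

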FI is a symptom requiring structural and functional assessment of the anal sphincter to direct choice of treatment. Structural assessment using AUS has been proven to be sensitive(12)(29). Functional assessment can result in a disparity between symptom profile and investigation findings(30) as well as an overlap of results between healthy and symptomatic persons(31). This was shown by Lam et al who identified no correlation between ARP and FI scores in a study of 218 patients. These findings were also reflected in a study undertaken by Zutshi et al on 53 symptomatic females(28). The role of investigatory tests is to guide treatment(30) and although these tests can establish a baseline , both HRAM and AUS are poor predictors of treatment outcome(32). This identifies a need for further study into the assessment of FI.

Novel techniques investigating other properties of the anal canal have been developed. These include assessing elasticity of the anal canal and anal acoustic reflectivity. These techniques are in their early stages and studies so far have shown limited clinical utilisation(33).

Electromyography (EMG) is a technique used to assess the innervation and response of a voluntary muscle fibre to a stimulus. Traditionally EMG is performed using a single needle electrode inserted into a muscle. Following stimulus to voluntarily contract, an action potential is generated along a somatic nerve resulting in a synapse at the neuromuscular junction (NMJ), also called innervation zone, and the release of acetylcholine (ACh). ACh acts on voltage gated channels in the sarcolemma causing depolarisation from the resting potential of -60—90 mV to + 75mV (motor unit potential) resulting in contraction of the muscle fibre. The EMG needle electrode detects the depolarization and records the amplitude (mV) and frequency (Hz). This provides information on individual motor unit potentials resulting from the innervation zone but limited information on overall muscular function. EMG of the EAS requires multiple circumferential punctures into the muscle this is both invasive and painful, limiting the investigation to research and specialist cases.

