The role of sEMG in clinical assessment of FI has been limited to research and has not been correlated with current gold standard techniques. This study aims to investigate the sEMG of symptomatic patients using MAPLe. The study will test the non-inferiority of MAPLe against HRAM and AUS in assessing FI. Non-inferiority of a test is defined as the test being no worse than the competitor. The study will aim to identify if particular patient groups have closer correlation

between symptom profiles and FI scores and sEMG results, and whether sEMG improves following treatment. The study will endeavor to identify the clinical utilisation of sEMG in FI.

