3.1 Assessment and Management of Risk

The table below summarise the risks and mitigations of all test above standard care that are being performed in a table:

Intervention	Potential risk	Risk Management
Assessment with MAPLe device	The device will be placed anally and record sEMG, not providing stimulation. As the device will be used in the same nature as current assessment devices no additional risk is perceived.	Performed by trained operator.

4. Objectives

Primary: To determine the role of MAPLe in the assessment of FI in defined patient groups.

Secondary: To determine if targeted treatment is achieved following assessment with MAPLe.

5. Trial design

This is cohort study of participants with symptoms of faecal incontinence. It will take place across two hospital trusts, both able to provide specialist pelvic floor services and facilities required to meet the needs of the study and follow up required by the participants. The use of two sites aims to increase the yield and diversity of participants. The sample size for the study is 120 participants.

Following a stringent selection and recruitment process, participants will be invited to a designated ARP session where they will be consented, complete an incontinence and quality of life questionnaire, and undergo ARP assessment. This will comprise of the current gold standard, AUS and HRAM, and additional assessment with MAPLe using a standardised protocol. Through undertaking all three tests participants will act at their own controls. Participant participation will conclude following ARP assessment unless treatment is deemed necessary by their local MDT. These participants will be followed up at 6 months with interval MAPLe assessment and incontinence and quality of life questionnaire.

The results will undergo statistical analysis to determine non-inferiority of MAPLe in assessing FI. For analysis participants will be allocated to the following groups: fistula/chronic perianal conditions, obstetric injury <12 months, obstetric injury >12months, neurogenic. Each group will be analysed using symptoms profile and MAPLe results to identify correlation. Comparison of MAPle results pre and post treatment will determine if targeted treatment has been achieved.

An expert panel of pelvic floor specialists will be formed to determine the additional benefit of MAPLe in a clinical context. The panel will consist of 3-6 specialists within the field. To reduce bias,

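### Agreement and correlation with HRAM (Section 11.5.1) measure resemblance to HRAM, so they cannot establish whether MAPLe is non-inferior to it in assessing faecal incontinence

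*Combined protocol and SAP*

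**What the plan says.** Section 3 (Rationale) sets the aim: "The study will test the non-inferiority of MAPLe against HRAM and AUS in assessing FI". It then gives the meaning of the term: "Non-inferiority of a test is defined as the test being no worse than the competitor". The Summary (Section 2) repeats the comparators: "MAPLe will be tested against HRAM and AUS".

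Section 11.5.1 names the method: "Non-inferiority testing of MAPLe will be performed using Bland-Altman method". In the same paragraph it adds, for the manometry comparison, "Correlation between MAPLe and HRAM for functional abnormalities will be identified". It states no margin, acceptable limits of agreement, correlation threshold, significance level or independent reference standard.

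Section 5 gives the comparators reference status: "This will comprise of the current gold standard, AUS and HRAM, and additional assessment with MAPLe". The Rationale takes a different view of manometry as a yardstick. It says "Functional assessment can result in a disparity between symptom profile and investigation findings", reports overlap between healthy and symptomatic people, cites a study of 218 patients with no correlation between physiology results and incontinence scores, and concludes that "both HRAM and AUS are poor predictors of treatment outcome".

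Other parts of the primary outcome do bring in something beyond HRAM. Section 11.1 includes the correlation of MAPLe with the symptom profile and the outcome of the expert panel. Panel Question 2 (Section 5) sets HRAM plus AUS against MAPLe plus AUS.

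**The concern.** The aim is a statement about performance in assessing FI. The method takes two inputs, the MAPLe reading and the HRAM reading, and no measure of FI enters. Agreement can stand in for performance only when the reference can be trusted. The protocol's reason for doing the study is that HRAM cannot be fully trusted. Where the two devices differ, the analysis cannot tell whether MAPLe or HRAM was wrong; where they agree, it cannot tell whether both were right.

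Some resemblance is also to be expected whatever MAPLe's merit. The HRAM and MAPLe protocols in the appendices use the same squeeze, endurance squeeze, push and cough manoeuvres, so shared patient effort alone can produce correlation.

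At stake is the conclusion of the primary analysis. A report that MAPLe is, or is not, non-inferior to HRAM would rest on statistics that do not bear on that question. The difficulty remains after both devices are put on a common scale and a margin is set. It is separate from the fact that one reads in mV and the other in mmHg.

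**Working it through.** **The plan's own figure.** Section 11.3 sets 4 groups × 30 = 120 participants, which reproduces. The 30 per group cannot be derived, because no significance level, power, effect size, standard deviation or margin is given. The argument in steps 1 to 3 does not depend on N; the precision of the remedy (step 4) does.

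**Notation.** On standardised scores, let rH be the correlation of HRAM with an independent FI criterion, v that of MAPLe with the same criterion, and ρ the MAPLe-HRAM correlation. The documents give none of these. All values below are assumptions, with rH varied from 0.2 to 0.7.

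**Step 1: how well could a perfect test agree with HRAM?** A perfect test equals the criterion, so ρ = rH. With rH = 0.3 it correlates 0.30 with HRAM. Its standardised 95% limits of agreement are ±1.96 × √(2(1 − 0.30)) = ±2.32 SD.

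**Step 2: what does close resemblance imply?** For given ρ and rH, the attainable range is v = ρ·rH ± √((1 − ρ²)(1 − rH²)). With ρ = 0.9 and rH = 0.3 this is 0.27 ± √(0.19 × 0.91) = 0.27 ± 0.416, that is −0.15 to 0.69. The limits of agreement are ±1.96 × √(2 × 0.1) = ±0.88 SD.

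| rH (assumed) | Perfect test's correlation with HRAM | Range of v when ρ = 0.9 |
|---|---|---|
| 0.2 | 0.20 | −0.25 to 0.61 |
| 0.3 | 0.30 | −0.15 to 0.69 |
| 0.5 | 0.50 | 0.07 to 0.83 |
| 0.7 | 0.70 | 0.32 to 0.94 |

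In every row the range for v includes values below and above rH. Even ρ = 0.9 leaves open whether MAPLe is worse, equal or better.

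**Step 3: same HRAM, same agreement, opposite merit.** Take rH = 0.3 and ρ = 0.5. Then v can lie anywhere in 0.15 ± √(0.75 × 0.91) = 0.15 ± 0.826, that is −0.68 to 0.98. A MAPLe with v = 0.1 (worse than HRAM) and one with v = 0.5 (better) are both possible. Both have limits of ±1.96 × √(2 × 0.5) = ±1.96 SD, so the agreement analysis cannot separate them.

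**Step 4: precision of a direct comparison.** Let d = v − rH, estimated in the same participants. In large samples

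Var(d) = [(1 − v²)² + (1 − rH²)²]/N − 2c, with c = [ρ(1 − v² − rH²) − ½·v·rH·(1 − v² − rH² − ρ²)]/N.

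Assume v = rH = 0.3 (no true difference) and one-sided 2.5%.

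- ρ = 0.3: N·Var(d) = 1.656 − 2 × 0.213 = 1.230. At N = 120 the standard error is 0.101 and the 95% half-width 0.198.
- ρ = 0.7: N·Var(d) = 1.656 − 2 × 0.559 = 0.538. At N = 120 the standard error is 0.067 and the half-width 0.131.

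| Margin | Power, N = 120 (ρ 0.3 to 0.7) | Power, n = 30 (ρ 0.3 to 0.7) | N for 80% power (ρ 0.3 to 0.7) |
|---|---|---|---|
| 0.20 | 51% to 85% | 17% to 32% | 242 to 106 |
| 0.10 | 17% to 32% | 7% to 11% | 966 to 423 |

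**The case against.** Four points can fairly be made for the plan.

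1. *Correlation is not called the non-inferiority test.* Section 11.5.1 attaches that label to Bland-Altman only. The Rationale notes that sEMG has not been correlated with current techniques, and filling that gap is a legitimate aim. This stands. The criticism of correlation is only that it cannot supply the missing evidence on performance.

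2. *There is no rule to pass or fail.* A reader might infer that an inferior device resembling HRAM would pass and a better one fail. The documents do not support that. They state no null hypothesis, threshold or acceptable limits, so no formal verdict exists. The direction of any error also depends on assumed inputs: a better device correlating 0.05 with HRAM has wide standardised limits (±2.70 SD), but one correlating 0.5 is equally possible and has limits of ±1.96 SD.

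3. *A look-alike may lose little.* If MAPLe were simply HRAM plus noise with ρ = 0.9 and rH = 0.3, its simulated AUC would be 0.622 against 0.636 for HRAM; with rH = 0.5, 0.706 against 0.730. This stands for that model. The ranges in step 2 show that close resemblance also permits much larger differences.

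4. *Benefit is judged on more than HRAM.* The MAPLe-symptom correlation and the expert panel soften the effect on the overall judgement. Neither fills the gap. No planned analysis sets MAPLe's relation to symptoms beside HRAM's. Section 11.5.1 assigns the panel to the clinical benefit of adding MAPLe, and Question 2 asks for confidence on the MAPLe set only.

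**Conclusion.** The concern holds in this form: Bland-Altman agreement and correlation with HRAM cannot establish whether MAPLe is worse than, equal to or better than HRAM in assessing FI, and no other planned analysis compares the two tests against a common FI criterion. This follows from what the methods take as input and from the protocol's own account of HRAM. It does not depend on the sample size, the units or the absence of a margin.

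The numbers illustrate the gap and are not estimates for this study. Under an assumed HRAM-criterion correlation of 0.3, a perfect test reaches only 0.30 with HRAM, and a MAPLe-HRAM correlation of 0.9 is compatible with a MAPLe-criterion correlation from −0.15 to 0.69. The conclusion is the same across the assumed range of 0.2 to 0.7. The documents do not support a claim that the plan would systematically favour a worse device or reject a better one. The plan should be changed before analysis, and the change is inexpensive.

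**What to change.** In Section 11.5.1 and the Summary, state that MAPLe-HRAM agreement and correlation are reported as concordance only, each as an estimate with a 95% confidence interval, and that no non-inferiority conclusion is drawn from them in either direction.

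Add a paired comparison in the same participants: the MAPLe-St Mark's association and the HRAM-St Mark's association, and the difference between these dependent correlations with its 95% confidence interval. Name in advance one summary reading per device, taken from a manoeuvre that both protocols include, and score both in the same direction. Report the two correlations as well as their difference: if HRAM's is close to zero, as the study of 218 patients cited in the Rationale suggests it may be, being no worse than HRAM would mean little.

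Claim non-inferiority only if a margin is fixed in advance and the interval excludes it.

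The cost is protocol wording and one further analysis. Appendix 1 already schedules HRAM, MAPLe and the incontinence questionnaire at Visit 2, so no new participants or procedures are needed. The downside is precision. Under the step 4 assumptions, 120 participants give 51% to 85% power for a margin of 0.20, and 30 per group give at most 32%. The difference is therefore best presented as an estimate with its interval, with the group results descriptive.
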